Initial Model ^a	Treatment A (N=X)	x	x.x	x.x	x.x, x.x	x.x, x.x	x.x	x.x, x.x	x.x, x.x	0.xxx
	Treatment B (N=X)	x	x.x	x.x	x.x, x.x	x.x, x.x				
Primary with Sensitivity Imputation ^b	Treatment A (N=X)	x	x.x	x.x	x.x, x.x	x.x, x.x	x.x	x.x, x.x	x.x, x.x	0.xxx
	Treatment B (N=X)	x	x.x	x.x	x.x, x.x	x.x, x.x				
Subgroup Analyses^c										
Baseline Ordinal Score										
5	Treatment A (N=X)	x	x.x	x.x	x.x, x.x	x.x, x.x	x.x	x.x, x.x	x.x, x.x	0.xxx
	Treatment B (N=X)	x	x.x	x.x	x.x, x.x	x.x, x.x				
6	Treatment A (N=X)	x	x.x	x.x	x.x, x.x	x.x, x.x	x.x	x.x, x.x	x.x, x.x	0.xxx
	Treatment B (N=X)	x	x.x	x.x	x.x, x.x	x.x, x.x				
5 or 6	Treatment A (N=X)	x	x.x	x.x	x.x, x.x	x.x, x.x	x.x	x.x, x.x	x.x, x.x	0.xxx
	Treatment B (N=X)	x	x.x	x.x	x.x, x.x	x.x, x.x				
Repeat for the rest of the subgroups in Table 6.										
CI=Confidence Intervals. N=Number of subjects in modified intent-to-treat (mITT) population. n= Number of unique subjects who progressed to mechanical ventilation or death that satisfies the row criteria. ^a Hazard Ratio (HR) is the hazard ratio calculated from the Cox Proportional Hazard Model comparing Active treatment vs Placebo and adjusting for the baseline dexamethasone use (yes, no), Baseline Ordinal Score (5, 6 or 7), age, and baseline CRP as covariates. All subjects whose last assessment was before Day 29 and were missing the event were censored at the date of last assessment. ^b Primary with Sensitivity Imputation: Same analysis as the initial model but subjects missing event and whose last assessment is before Day 29 are non-events for good discharges and censored at Day 29 or at last assessment for subjects still hospitalized or discharged to LTAC, hospice care, or other hospital. ^c For the subgroup analyses, the model described in ^a was performed for each level of the subgroup. ^d Number of subjects who progressed to a clinical status of 7 or 8 through Day 29. ^e P-value is based on the adjusted cox model.										

Table with similar format:

Table 43: Time to Mechanical Ventilation or Death through Day 29 — mITT Population

[Implementation note: Add subgroup category for baseline ordinal score 7 and baseline ordinal score ‘6 or 7’ to Table 43.]

Table 44: Z-Scores and Westfall-Young Permutation P-Value Adjustment — mITT Population

[Implementation note: This analysis is option and will be performed only if its inclusion appears likely to be helpful in interpreting the primary and secondary analyses results.]

Endpoint	Raw P-value	Westfall-Young Adjusted P-Value
Analysis Including Day 8 OS as a Continuous Endpoint		
Clinical Status at Study Day 8	0.xxx	0.xxx
Sustained Survival Without Respiratory Failure	0.xxx	0.xxx
Difference from Baseline Clinical Status at Days 3	0.xxx	0.xxx
Difference from Baseline Clinical Status at Days 5	0.xxx	0.xxx
Difference from Baseline Clinical Status at Days 8	0.xxx	0.xxx
Difference from Baseline Clinical Status at Days 11	0.xxx	0.xxx
Difference from Baseline Clinical Status at Days 15	0.xxx	0.xxx
Difference from Baseline Clinical Status at Days 22	0.xxx	0.xxx
Difference from Baseline Clinical Status at Days 29	0.xxx	0.xxx
Number of Days Clinical Status >4	0.xxx	0.xxx
Number of Days Clinical Status >5	0.xxx	0.xxx
Number of Days Clinical Status >6	0.xxx	0.xxx
Value of CRP	0.xxx	0.xxx
Value of Ferritin	0.xxx	0.xxx
Value of D-dimer	0.xxx	0.xxx
Value of Fibrinogen	0.xxx	0.xxx
Value of LDH	0.xxx	0.xxx
14-Day Mortality	0.xxx	0.xxx
28-Day Mortality	0.xxx	0.xxx
59-Day Mortality	0.xxx	0.xxx
Repeat above analyses excluding the Day 8 OS endpoint		
Note: This analysis will be based on complete data.		

Table 45: Hochberg P-Value Adjustment — mITT Population

[Implementation note: This analysis is option and will be performed only if its inclusion appears likely to be helpful in interpreting the primary and secondary analyses results.]

Endpoint	Raw P-value ^a	Hochberg Adjusted P-Value	Z-Scores	Global P-Value
Clinical Status at Study Day 8	0.xxx	0.xxx	x.xx	0.xxx
Time (days) to Sustained Recovery	0.xxx	0.xxx	x.xx	
Sustained Survival Without Respiratory Failure	0.xxx	0.xxx	x.xx	
Time (days) to at least 1 point Improvement from Baseline	0.xxx	0.xxx	x.xx	
Time (days) to at least 2 point Improvement from Baseline	0.xxx	0.xxx	x.xx	
Difference from Baseline Clinical Status at Days 3	0.xxx	0.xxx	x.xx	
Difference from Baseline Clinical Status at Days 5	0.xxx	0.xxx	x.xx	
Difference from Baseline Clinical Status at Days 8	0.xxx	0.xxx	x.xx	
Difference from Baseline Clinical Status at Days 11	0.xxx	0.xxx	x.xx	
Difference from Baseline Clinical Status at Days 15	0.xxx	0.xxx	x.xx	
Difference from Baseline Clinical Status at Days 22	0.xxx	0.xxx	x.xx	
Difference from Baseline Clinical Status at Days 29	0.xxx	0.xxx	x.xx	
Number of Days Clinical Status >4	0.xxx	0.xxx	x.xx	
Number of Days Clinical Status >5	0.xxx	0.xxx	x.xx	
Number of Days Clinical Status >6	0.xxx	0.xxx	x.xx	
Value of CRP	0.xxx	0.xxx	x.xx	
Value of Ferritin	0.xxx	0.xxx	x.xx	
Value of D-dimer	0.xxx	0.xxx	x.xx	
Value of Fibrinogen	0.xxx	0.xxx	x.xx	
Value of LDH	0.xxx	0.xxx	x.xx	
14-Day Mortality	0.xxx	0.xxx	x.xx	
28-Day Mortality	0.xxx	0.xxx	x.xx	
59-Day Mortality	0.xxx	0.xxx	x.xx	
Time (days) to Death	0.xxx	0.xxx	x.xx	

^a Raw p-values and Z-scores will come from analysis of these endpoints using multiple imputation for Day 8 Ordinal Score and using complete data for the rest of the endpoints.

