4. INVESTIGATIONAL PLAN

4.1. Overall Study Design and Plan

This is a platform trial to conduct a series of randomized, double-blind, placebo-controlled trials using common assessments and endpoints in hospitalized adults diagnosed with COVID-19. This is a proof-of-concept study with the intent of identifying promising treatments to enter a more definitive study (such as Adaptive COVID-19 Treatment Trial [ACTT], Accelerating COVID-19 Therapeutic Interventions and Vaccines [ACTIV], industry sponsored trials etc.). The study will be conducted at up to 70 domestic sites and 5 international sites. The study will compare different investigational therapeutic agents to a common control arm and determine which have relatively large treatment effects. In order to maintain the double blind, each intervention will have a matched placebo. However, the control arm will be shared between stages/interventions and may include participants receiving the matched placebo for a different stage/intervention.

The general goal of the stages included in this platform trial is not to determine clear statistical significance for an intervention, but rather to determine which products yield clinical data suggestive of efficacy and should be moved quickly into larger studies. However, clinical or drug development priorities may arise that require a larger sample size and a plan for a more definitive study. Estimates produced from this trial will provide an improved basis for designing the larger trial, in terms of sample size and endpoint selection. Products with little indication of significant efficacy will be dropped on the basis of interim evaluations. In addition, some interventions may be discontinued on the basis of interim futility or efficacy analyses.

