4.4.3. Method of Assigning Subjects to Treatment Groups (Randomization)

Randomization will be stratified by study site and severity measured by baseline ordinal score (baseline ordinal score of 5 versus a baseline ordinal score of 6 or 7).

Subjects will first be randomized to 1 of the stages to which they are eligible with equal allocation. Then patients are randomized to the active intervention or placebo version of that stage with allocation $k:1$, where k is the number of interventions for which a subject is eligible. For example, if a subject is eligible for 3 active interventions or stages that the site is currently randomizing, the subject will be randomized to 1 stage with a 1:1:1 allocation to the 3 stages, then randomized to the selected intervention's or stage's active or placebo arm with a 3:1 allocation of active versus placebo. This process results in equal allocation of the 3 active intervention arms and the pooled placebo arm.

Differing entry criteria across interventions adds complexity to this process. Subjects who are eligible for all 3 interventions will be randomized to A, B, or C in the first randomization step, and then have a 25% chance of randomization to placebo in the second step. However, the subject who is not eligible for C will first be randomized to stages with A or B with equal probability, and will have a 33% chance of randomization to placebo in the second step, leading to equal size A, B, and pooled placebo groups for this stratum of subjects. Ultimately, evaluation of A versus placebo would need to only include subjects that were eligible to be randomized to A.

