5. SAMPLE SIZE CONSIDERATIONS

We have chosen a sample size of 100 per arm for the proof of concept stages. The power can be computed for the Study Day 8 ordinal score on the basis of an odds ratio representing clinical improvement. The odds ratio represents the odds of improvement in the ordinal scale for treatment relative to placebo. The sample size to detect a given odds ratio for 1:1 randomization using a 2-tailed test at level α is given by

$$\frac{12(z_{\alpha/2} + z_{\beta})^2}{\lambda^2(1 - \sum_{i=1}^K p_i^3)}$$

where λ is the log odds ratio, p_i is the overall probability (combined over both arms) of being in the i^{th} category of the K ordinal outcomes, $z_{\alpha/2}$ and z_{β} are the $1 - \alpha/2$ and $1 - \beta$ quantiles, respectively, of the standard normal distribution.

However, to fully understand all aspects of the testing procedure, we have simulated the probabilities of an intervention: a) being declared futile after 50 subjects per arm, b) being declared efficacious after 50 subjects per arm, and c) being declared promising by 100 subjects per arm.

The interim analysis will find an intervention futile if its point estimate for the primary endpoint has an odds ratio <1 . An intervention can be declared efficacious early after 50 subjects per arm if two-sided $p < 0.001$ and $OR > 1$. If the intervention continues to 100 subjects, it will be declared promising if the final p -value is < 0.20 and $OR > 1$, and statistically significant if the final p -value is < 0.05 . More details are provided in Interim Analysis Section.

Table 4 displays the outcome probabilities in the control arm for sample size determination; this uses preliminary unpublished data from the remdesivir arm in ACTT study. The categories of the 8-point ordinal scale are described in Section 3.2.

Table 4: Expected distribution of ordinal outcomes for the control arm at Study Day 8

Severity Outcome	Outcome (%)
1. Not hospitalized, no new or increased limitations on activities	0.0
2. Not hospitalized, but new or increased limitation on activities and/or requiring new or increased home oxygen, CPAP or BiPAP	34.6
3. Hospitalized, not requiring new or increased supplemental oxygen - no longer requires ongoing medical care	1.2
4. Hospitalized, not requiring new or increased supplemental oxygen - requiring ongoing medical care (COVID-19 related or otherwise)	10.6
5. Hospitalized, requiring new or increased supplemental oxygen	17.1

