6. GENERAL STATISTICAL CONSIDERATIONS

6.1. General Principles

This is a proof of concept double-blind placebo controlled randomized trial testing a superiority hypothesis where interventions with a two-sided p-value $< .20$ will be declared promising and will be considered statistically significant if the final two-sided p-value is $< .05$. These data will be summarized by treatment (intervention name versus placebo) and when appropriate by baseline ordinal score. Additionally, data will be described according to the appropriate summary statistics, e.g.

- Percentages/proportions/odds ratios for categorical data. For tabular summaries of percentages/proportions, the denominator (e.g., number of subjects in the specified population) will be displayed.
- Means, standard deviation, median, and/or range for continuous data, median and confidence intervals for time-to-event data.

Confidence intervals will be generated; 95% and 80% confidence intervals will be generated for primary and key secondary outcomes. For hazard ratio and odds ratio estimates, Wald confidence intervals will be used. For confidence intervals of proportions for other efficacy and safety outcomes, Blaker confidence intervals will be used.

In general, all tables will have corresponding listings of data presented unless noted otherwise.

When calculating treatment effects (e.g., differences, hazard ratios, odds ratios) from regression modelling, placebo will be used as the reference group. Subjects on interventions will only be compared to control subjects who could potentially have been randomized to that intervention (i.e., they met eligibility criteria for the intervention and are at a site where the intervention was enrolling at the time of the subject's randomization). Analyses of newly added arm(s) will be performed comparing concurrently enrolled control subjects. For any modeling that uses covariates defined in Section 6.4, the category listed last for each variable in that section will be used as the control group for the interaction analysis and covariate-adjusted analyses.

For the time-to-event analyses, the following SAS pseudocode will be used to generate stratum-specific median time to event estimates and confidence intervals and stratum-specific Kaplan-Meier curves.

```
proc lifetest data=dataset plots=(s);
  time timevariable * censorvariable(1);
  test treatmentvariable;
run;
```

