In this approach, `timevariable` represents the time until the event in question (e.g., recovery), `censorvariable` represents the censoring variable (e.g., 0= event observed, 1= event did not occur at the time of withdrawal, discharge, lost-to-followup, etc), and `treatmentvariable` represents the intervention (e.g., 0= remdesivir + placebo, 1= remdesivir + new treatment).

To perform a Cox proportional hazards analysis and generate the treatment hazard ratio along with its Wald confidence interval and p-value from the score test after adjusting for other covariates, the following SAS pseudocode will be used.

```
proc phreg data=dataset;
  class treatmentvariable(ref=placebolabel) othercovariates;
  model timevariable * censorvariable(1) = treatmentvariable othercovariates /
  ties=efron;
  hazardratio treatmentvariable / diff=ref cl=wald;
```

```
ods output hazardratios = hrest globaltest=pvalue;
run;
```

To assess the assumption of proportional hazards for Cox models, Kaplan-Meier curves for each treatment arm will be produced (PH assumption supported if curves do not cross). Restricted mean survival time along with its 95% CI will be reported to assess whether the results change if the PH assumption is not satisfied.

Proportional Odds analysis without MI:

The following SAS pseudocode will be used to perform the proportional odds analysis with treatment, baseline ordinal score and baseline steroid use as covariates to generate the treatment odds ratio, p-value, and predicted probabilities of the ordinal scale levels by treatment and ordinal score using complete data

```
proc logistic data=dataset out=imp_parms plots(only)=effect(x= ordscore_d8
  sliceby =baseordscorevar*trtvar individual connect);
  class baseordscorevar (param=ref ref=5) basesteroidusevar (param=ref ref=no
steroid use) trtvar (param=ref ref=placebolabel);
  model ordscore_d8 = trtvar baseordscorevar basesteroidusevar;
  oddsratio trtvar;
  ods output oddsratioswald = orest;
run;
```

For the endpoints analyzed by proportional odds, odds ratios between the binary progression strata will be computed, to support data understanding. For example, odds ratio, confidence intervals from logistic regression will be reported for treatment effect for the binary endpoint of OS= 1-7 vs 8, then OS= 1-6 vs 7-8, etc. Similar odds ratios across these 7 2x2 tables will support the proportional odds assumption.

95% Blaker confidence intervals for proportions/percentages:

```
proc freq;

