	Treatment A (N=X)	6	x	x	x.x	x.x, x.x	x.x, x.x	x.xx	x.xx, x.xx	x.xx, x.xx
	Treatment B (N=X)		x	x	x.x	x.x, x.x	x.x, x.x			
	Treatment A (N=X)	7	x	x	x.x	x.x, x.x	x.x, x.x	x.xx	x.xx, x.xx	x.xx, x.xx
	Treatment B (N=X)		x	x	x.x	x.x, x.x	x.x, x.x			
	Treatment A (N=X)	Any BOS	x	x	x.x	x.x, x.x	x.x, x.x	x.xx	x.xx, x.xx	x.xx, x.xx
	Treatment B (N=X)		x	x	x.x	x.x, x.x	x.x, x.x			

N = Number of subjects in the specified treatment group, actual baseline ordinal score, and analysis population.

n = Number of recovered subjects.

Difference is the difference in the restricted mean recovery time between active treatment to placebo.

^a Tau is the truncation time point for the Restricted Mean Survival Time analysis and is equal to the minimum of the largest observed times in each group.

Programming

Within an actual baseline ordinal score stratum:

```
proc lifetest data=enrevent plots=(rmst) method=breslow rmst(cl);
by stratum;
time evntday * Censor(1);
strata trtcode /diff=all;
ods output rmst=rmst;
run;
```

Table 30: Proportion of Subjects Alive and Without Respiratory Failure through Day 29 — mITT Population

Analysis/Subgroup	Category	Treatment A (N=x)		Treatment B (N=x)		Odds Ratio			Risk Difference ^g			P-value ^h
		n	% (95%CI) ^f	n	% (95%CI) ^f	Estimate	95% CI	80% CI	Estimate	95% CI	80% CI	
Initial model, Age, Baseline OS, Dexamethasone Use, and CRP ^a	-	x	x.x (x.x, x.x)	X	x.x (x.x, x.x)	x.x	x.x, x.x	x.x, x.x	x.x	x.x, x.x	x.x, x.x	0.xxx
Primary with Sensitivity Imputation 1 ^b	-	x	x.x (x.x, x.x)	X	x.x (x.x, x.x)	x.x	x.x, x.x	x.x, x.x	x.x	x.x, x.x	x.x, x.x	0.xxx
Sensitivity Analysis 1: Baseline OS and Steroid Use ^c	-	x	x.x (x.x, x.x)	x	x.x (x.x, x.x)	x.x	x.x, x.x	x.x, x.x	x.x	x.x, x.x	x.x, x.x	0.xxx
Supplemental Analysis 1: Impact of age and duration of symptoms prior to enrollment ^d	-	x	x.x (x.x, x.x)	x	x.x (x.x, x.x)	x.x	x.x, x.x	x.x, x.x	x.x	x.x, x.x	x.x, x.x	0.xxx
Subgroup Analyses^e												
Baseline Ordinal Score	5	x	x.x (x.x, x.x)	x	x.x (x.x, x.x)	x.x	x.x, x.x	x.x, x.x	x.x	x.x, x.x	x.x, x.x	0.xxx
	6 or 7	x	x.x (x.x, x.x)	x	x.x (x.x, x.x)	x.x	x.x, x.x	x.x, x.x	x.x	x.x, x.x	x.x, x.x	0.xxx
Repeat for all subgroups from Table 6		x	x.x (x.x, x.x)	x	x.x (x.x, x.x)	x.x	x.x, x.x	x.x, x.x	x.x	x.x, x.x	x.x, x.x	0.xxx

CI=Confidence Internals. OR=Odds Ratios. NA=Not applicable.

N=Number of subjects in the modified-intent-to-treat (mITT) population. n=Number of subjects without respiratory failure or death through Day 29.

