		Treatment B (N=X)	X	x.x	x.xx	x.x, x.x	x.xxx								
	7	Treatment A (N=X)	X	x.x	x.x	x.x, x.x	x.xxx	x.x	x.x, x.x	x.x, x.x	x.x	x.x, x.x	x.x, x.x	0.xxx	

Analysis Type	Baseline Ordinal Score	Treatment Group	Number of Deaths		Mortality Rate (CI) ^c			Difference in Mortality Rates at the Specified Time Point ^d			HR ^e			P-value ^f
			n	%	Estimate	80% CI	95% CI	Estimate	80% CI	95% CI	Estimate	80% CI	95% CI	
		Treatment B (N=X)	X	x.x	x.xx	x.x, x.x	x.xxx							
	Any BOS	Treatment A (N=X)	X	x.x	x.x	x.x, x.x	x.xxx	x.x	x.x, x.x	x.x, x.x	x.x	x.x, x.x	x.x, x.x	0.xxx
		Treatment B (N=X)	X	x.x	x.xx	x.x, x.x	x.xxx							

CI= Confidence Intervals. N=Number of subjects in the Safety population. n= Number of unique subjects that satisfies the row criteria.

^a For the primary endpoint, all subjects whose last assessment was before the corresponding timepoint (Day 15 Visit, Day 29 Visit, Day 60 Visit) and were missing the event were censored at the date of last assessment.

^b Primary with Sensitivity Imputation: Same analysis as the initial model but subjects missing event and whose last assessment is before the corresponding timepoint (Day 15 Visit, Day 29 Visit, Day 60 Visit) are non-events for good discharges and censored at Day 15, Day 29, Day 60 respectively or at last assessment for subjects still hospitalized or discharged to LTAC, hospice care, or other hospital.

^c Mortality Rates are the Kaplan-Meier estimates.

^d Difference in mortality rates (80%, 95% CI) obtained from Kaplan Meier.

^e HR is the hazard ratio from the Cox Proportional Hazard Model adjusted for baseline ordinal score and baseline steroid use.

^f P-value is based on the Cox adjusted model.

Table 55: Time to Death through Day 15, 29, or 60 by Treatment Group: Restricted Mean Survival Time Analysis — Safety Population

Study Day	Treatment Group	Actual Baseline Ordinal Score	n	Restricted Mean Mortality Time (Days)		Difference	
				Estimate	95% CI	Estimate	95% CI
Day 15	Treatment A (N=X)	5	x	x.x	x.x, x.x	x.xx	x.xx, x.xx
	Treatment B (N=X)		x	x.x	x.x, x.x		
	Treatment A (N=X)	6	x	x.x	x.x, x.x	x.xx	x.xx, x.xx
	Treatment B (N=X)		x	x.x	x.x, x.x		
	Treatment A (N=X)	7	x	x.x	x.x, x.x	x.xx	x.xx, x.xx
	Treatment B (N=X)		x	x.x	x.x, x.x		
	Treatment A (N=X)	Any BOS	x	x.x	x.x, x.x	x.xx	x.xx, x.xx
	Treatment B (N=X)		x	x.x	x.x, x.x		

Repeat for Day 29 and Day 60

N= Number of subjects in the specified treatment group, actual baseline ordinal score, and analysis population.

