n = Number of subjects who died by the specified study day.

Difference is the difference in the restricted mean mortality time between Active treatment and Placebo.

Table 56: Time to Death, SAE or Grade ≥ 3 TEAEs through Day 60 — Safety Population

Baseline Ordinal Score	Treatment Group	Number of Deaths or Grade >3 TEAEs		Event Rate (CI) ^a			Difference in Event Rates at the Specified Time Point ^b			HR ^c			P-value ^d
		n	%	Estimate	80% CI	95% CI	Estimate	80% CI	95% CI	Estimate	80% CI	95% CI	
5	Treatment A (N=X)	X	x.x	x.x	x.x, x.x	x.xxx	x.x	x.x, x.x	x.x, x.x	x.x	x.x, x.x	x.x, x.x	0.xxx
	Treatment B (N=X)	X	x.x	x.xx	x.x, x.x	x.xxx							
6	Treatment A (N=X)	X	x.x	x.x	x.x, x.x	x.xxx	x.x	x.x, x.x	x.x, x.x	x.x	x.x, x.x	x.x, x.x	0.xxx
	Treatment B (N=X)	X	x.x	x.xx	x.x, x.x	x.xxx							
7	Treatment A (N=X)	X	x.x	x.x	x.x, x.x	x.xxx	x.x	x.x, x.x	x.x, x.x	x.x	x.x, x.x	x.x, x.x	0.xxx
	Treatment B (N=X)	X	x.x	x.xx	x.x, x.x	x.xxx							
Any BOS	Treatment A (N=X)	X	x.x	x.x	x.x, x.x	x.xxx	x.x	x.x, x.x	x.x, x.x	x.x	x.x, x.x	x.x, x.x	0.xxx
	Treatment B (N=X)	X	x.x	x.xx	x.x, x.x	x.xxx							

CI= Confidence Intervals. N=Number of subjects in the Safety population. n= Number of unique subjects that satisfies the row criteria.

^a Event rates are the Kaplan-Meier estimates.

^b Difference in event rates (80%, 95% CI) obtained from Kaplan Meier.

^c HR is the hazard ratio from the Cox Proportional Hazard Model adjusted for baseline ordinal score and baseline steroid use.

^d P-value is based on the Cox adjusted model.

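### The overall ('Any BOS') restricted-mean difference in SAP Table 29 has no severity-stratified or adjusted estimator, so it is less precise than it need be and is not a like-for-like check on the adjusted Cox result

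*SAP*

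**What the plan says.** On design, SAP 4.4.3 states: "Randomization will be stratified by study site and severity measured by baseline ordinal score", the severity split being score 5 against 6 or 7.

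On the main analysis of time to sustained recovery, SAP 6.4.2 specifies a Cox model with baseline steroid use and actual baseline ordinal score as covariates.

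On the check, SAP 6.1 states: "Restricted mean survival time along with its 95% CI will be reported to assess whether the results change if the PH assumption is not satisfied".

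On how the RMST difference is formed, SAP 8.2.1 describes treatment differences within each baseline-score stratum and nothing else; SAP 9.4 does the same for mortality. The Table 29 shell goes further. For both mITT and ITT it has rows for scores 5, 6 and 7 and an 'Any BOS' row, each with a difference and 95% and 80% intervals. Its footnote reads "Difference is the difference in the restricted mean recovery time between active treatment to placebo". The programming note is labelled for use within a stratum and has treatment as its only STRATA variable. The truncation time tau is the smaller of the arms' largest observed times.

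Tables 54 and 55 also carry 'Any BOS' rows for death, footnoted "Difference in mortality rates (80%, 95% CI) obtained from Kaplan Meier" and "Difference is the difference in the restricted mean mortality time between Active treatment and Placebo" respectively.

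**The concern.** If severity predicts recovery, a pooled two-arm comparison counts the spread between severity groups as noise, although the randomisation strata and the Cox model both take account of severity. The interval for the one overall RMST difference is then wider than it need be.

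It also weakens the check. Moving from the Cox hazard ratio to the 'Any BOS' RMST difference changes the effect measure and drops severity and steroid adjustment in the same step. If the two results look different, the reader cannot tell whether non-proportional hazards or the lost covariates are responsible.

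**Working it through.** **1. The plan's own figure.** The documents give no precision or power figure for any RMST or Kaplan-Meier difference. The nearest design figure is Table 5. Simulating the Table 4 distribution with the stated interim rule at an odds ratio of 2 gives power 0.758 at alpha .05 (stated 0.765) and 0.909 at alpha .20 (stated 0.913), so the basic design inputs are read correctly.

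**2. Inputs.** From the SAP: 100 per arm ("We have chosen a sample size of 100 per arm for the proof of concept stages"); follow-up to Day 60; 35.8% of controls in categories 1 to 3 at Day 8 (Table 4: 0 + 34.6 + 1.2). Assumed, because the documents do not say: half the subjects in each stratum, exponential recovery, a within-stratum hazard ratio of 1.5, no losses, and Day 8 recovery rates by stratum that average 35.8%.

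**3. Formulas.** Recovery rate λ = −ln(1 − p)/8, where p is Day 8 recovery. Restricted mean to 60 days = (1 − e^(−60λ))/λ. With stratum weights w and 1 − w, and severity balanced between arms,

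reported variance (pooled) = variance (stratified) + w(1 − w)(Δ₀² + Δ₁²)/100,

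where Δ₀ and Δ₁ are the differences in restricted mean between severity strata in the placebo and active arms.

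**4. One case in full: 55% vs 17% (16.6%) recovered at Day 8.** λ = 0.0998 and 0.0227 on placebo. Restricted means are 9.99 and 32.78 days on placebo, 6.68 and 25.57 on active. The within-stratum differences are −3.32 and −7.21, average −5.26 days. Pooled and stratified estimators both target this number. Δ₀ = 22.78 and Δ₁ = 18.89, so the extra variance is 0.25 × (22.78² + 18.89²)/100 = 2.19. The stratified variance is 4.96, so the pooled variance is 7.15. The 95% widths are 3.92 × √4.96 = 8.73 and 3.92 × √7.15 = 10.48 days, a ratio of 1.20. Simulation gave 8.72 and 10.48.

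**5. Range (simulation, 6,000 runs per setting, blocked by severity; last column blocked by site and severity).**

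| Day 8 recovery, score 5 vs 6/7 | Width, pooled | Width, stratified | Excess | Pooled 95% coverage, severity blocks | Pooled 95% coverage, 75 sites × severity |
|---|---|---|---|---|---|
| 40% vs 32% | 7.79 | 7.71 | 1% | 95.6% | 94.9% |
| 45% vs 27% | 8.35 | 7.97 | 5% | 96.0% | 94.5% |
| 55% vs 17% | 10.48 | 8.72 | 20% | 97.8% | 95.7% |
| 65% vs 7% | 13.45 | 8.29 | 62% | 99.8% | 97.5% |

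The stratified interval covered 94.2% to 95.5% throughout.

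A second set of assumptions, with a fraction who never recover, gave variance cuts of 19% (median 6 vs 14 days, 5% vs 25% never recovering), 32% (6 vs 20 days, 5% vs 35%) and 43% (5 vs 25 days, 5% vs 40%). As excess width, 1/√(1 − cut) − 1, these are 11%, 21% and 32%. Where severity matters little (8 vs 12 days, 10% vs 20%) the excess was about 2%. The excess width was much the same with 1, 20 or 75 sites.

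**6. The like-for-like question.** With a within-stratum hazard ratio of 1.5, a Cox model without severity gave 1.44, 1.35 and 1.24 in the last three rows of the table; with severity it gave 1.50, 1.47 and 1.49. Dropping severity therefore moves a Cox result even when hazards are proportional within strata. The RMST difference keeps its target and loses only precision.

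**7. Mortality.** Ratio of widths = √[p̄(1 − p̄) / mean of p(1 − p) within strata]. For assumed Day 29 mortality of 4% vs 12%: √(0.0736/0.0720) = 1.01. For 4% vs 20%: √(0.1056/0.0992) = 1.03. For 3% vs 35%: √(0.1539/0.1283) = 1.10.

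**The case against.** The SAP text already plans the RMST differences that respect severity, within strata, and Table 29 prints them. The 'Any BOS' difference is a shell row with no code of its own, so calling it a plain two-arm comparison is an inference. This stands: what is missing is one overall difference that respects severity. The separate rows do not fill the gap, because they split 6 from 7 while randomisation and the Cox covariate use 5 against 6/7.

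A reader might infer that the pooled intervals are wrong, that they over-cover badly, or that significance could be lost. The documents do not support this. The pooled difference is a valid marginal effect. Tables 29 and 55 have no p-value column, so no RMST test is planned. Strong over-coverage needs near-perfect severity balance, whereas randomisation is also stratified by site: "The study will be conducted at up to 70 domestic sites and 5 international sites". That allows up to 75 × 2 = 150 cells for about 200 subjects, and coverage with 75 sites stayed near 95% except in the extreme case.

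Severity weighting alone would still omit steroid use, so only a covariate-adjusted RMST difference matches the Cox model. No decision rule uses Table 29; the promising threshold applies to the Day 8 model, which already adjusts for severity. That limits the consequence but does not justify the less precise estimator.

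**Conclusion.** The point holds for the 'Any BOS' row of Table 29. As written, the overall RMST difference is valid but less precise than one that respects the randomisation stratum, and it differs from the Cox model in covariates as well as in effect measure. The excess width runs from 1% or 2% if severity barely predicts recovery to about 32% if it predicts strongly, and to 62% in the extreme case. These figures rest on assumed recovery rates, equal strata and no losses, so the true size cannot be fixed from the documents. Over-coverage is a lesser matter and shrinks as the number of site-by-severity cells grows. For the mortality difference the excess is only about 1% to 10%, so Tables 54 and 55 do not carry the point.

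**What to change.** For the 'Any BOS' row of Table 29, specify one of two estimators:

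- a severity-stratified RMST difference (5 vs 6/7): the average of the within-stratum differences weighted by stratum size, with variance equal to the sum of squared weights times the stratum variances; or
- an RMST difference adjusted for baseline ordinal score and steroid use, which matches the Cox model.

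Three details are needed for either to work. Set one common tau across strata and arms, because differences with row-specific tau cannot be averaged. Estimate the combined 6/7 stratum, which is not a row in the shell. State which stratum takes subjects with an actual baseline score of 4, whom other shells (for example Tables 12 and 13) count in 'Any BOS'. Keep the unadjusted row as description.

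The cost is SAP and shell wording and a modest amount of code, with no new data.

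Doing the same in Tables 54 and 55 is optional. Sparse deaths can make a stratum variance zero: at an assumed mortality of 2% to 4% with 50 per arm in a stratum, the chance of no deaths in a given arm is 0.98⁵⁰ = 36% to 0.96⁵⁰ = 13%.

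Separately, reconcile Table 6, which states no covariate adjustment for time to death by Day 29, with SAP 9.4 and the Table 54 footnote, which give a Cox model adjusted for baseline ordinal score and steroid use.
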